3. STUDY DESIGN

As described below active participation in the study (involving a single visit to the hospital) will last a total of 1 day, while the access (and analysis) of follow-up data generated as part of routine care pathway will go on for a period of 18 months in total. Participants are not required to do anything during this segment of the study.

- Observational cohort study
- 40 Primary open-angle and normal tension glaucoma patients will be attending a single visit lasting 9 hours.
- Their usual follow-up data will be tracked for 18 months

3.1 STUDY OUTCOME MEASURES

- **Primary outcome measure:**

Intraocular pressures measured during the mDTC
Intraocular pressures measured during the WDT

- **Secondary outcome measures:** postural blood pressure, heart rate, pupil diameter, pulse oximetry, OCT imaging parameters (angiography and anterior segment angle size) including current and future rates of progression using nerve fibre layer thickness on optical coherence tomography (OCT) and visual field testing.

3.1.1. Premedication

No premedication is required in this study; however, the assessment of the intraocular pressure requires the surface of the eye to be anaesthetised by means of topical drops.

Proxymetacaine hydrochloride 0.5% drops are used for that purpose; the drops have been in approved use for a number of years and are part of standard of care.

3.1.2. Interventions

Baseline and qualification assessments will take place on the day of the study. These include a medical, ophthalmic and drug history, ophthalmic examination, postural blood pressure measurement, testing of visual acuity, OCT/OCTA of the optic disc and macula and then IOP assessment. All ophthalmic assessments will be done on both eyes using the Heidelberg Spectralis® imaging system. The mDTC will be conducted as part of patient's regular visit and is standard of care which consists of 5 IOP measurements beginning at 8am and 2 hourly afterwards (+/- 15min). Following completion of mDTC patients will have their WDT as detailed below.

The water drinking test will occur following the mDTC and will involve the patient drinking 800mL of water at room temperature, within a maximum of five minutes, after a period of no fluid intake of at least 2 hours. This will come after a period of no fluid intake of at least 2 hours (2pm onwards). For the WDT, the first IOP measure will correspond to the last mDTC measure, and three IOP measurements will be made after water intake with a 15-minute interval between each. IOP measurements will be recorded using Goldmann Applanation Tonometry (GAT). At each 15 minute interval, postural blood pressure, heart rate, oxygen saturations and pupil diameter will be measured. The ambient light conditions will be monitored with a light meter. Imaging will then be repeated after one hour of the test.

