3.1.1. Premedication	12
3.1.2. Interventions	13
4. PARTICIPANT ENTRY	13
4.1 INCLUSION CRITERIA	13
4.2 EXCLUSION CRITERIA	13
4.3 WITHDRAWAL CRITERIA	14
5. ADVERSE EVENTS	14
5.1 DEFINITIONS	14
5.3 REPORTING PROCEDURES	14
6. ASSESSMENT AND FOLLOW-UP	15
7.1 SAMPLE SIZE	15
7.2 RECRUITMENT	15
7.3 FOLLOW-UP	16
7.4 DATA ANALYSIS	16
7.4.1. Data Collection	16
7.4.2. Data Management	16
7.4.3. Statistical analysis	16
8. REGULATORY ISSUES	16
8.1 ETHICS APPROVAL	16
8.2 CONSENT	17
8.3 CONFIDENTIALITY	17
8.4 INDEMNITY	17
8.5 SPONSOR	17
8.6 FUNDING	17
8.7 AUDITS	17
9. STUDY MANAGEMENT	17

10. PUBLICATION POLICY	17
APPENDIX 1. PARTICIPANT TIMELINE	18

GLOSSARY OF ABBREVIATIONS

DTC – Diurnal Tension Curve

GCC – Ganglion Cell Complex

IOP – Intraocular Pressure

MD – Mean Deviation

mDTC – modified Diurnal Tension Curve

NFL – Nerve Fiber Layer

NTG – Normal Tension Glaucoma

OCT – Optical Coherence Tomography

VF – Visual Field

WDT – Water Drinking Test

[figure not shown]
KEYWORDS

Intraocular pressure, stress test, correlation, water drinking test, modified diurnal tension curve, glaucoma progression, OCT, VF, normal tension glaucoma

STUDY SUMMARY

TITLE	The Water Drinking Test (WDT) in Glaucoma Study: WIGS
DESIGN	Observational cohort study
AIMS	To investigate the correlation and agreement between the intraocular pressure peaks detected during the water drinking test and modified diurnal tension curve in glaucomatous eyes and to analyse whether this is associated with prognostic outcome. We will also measure autonomic nervous system activation during the test to investigate one possible mechanism behind it.
OUTCOME MEASURES	Peak IOP measurements from the two different methods
POPULATION	Primary open-angle and normal tension glaucoma patients
ELIGIBILITY	Primary open-angle and normal tension glaucoma patients, not on anti-ocular hypertensive therapy.
	
- Able to give informed consent to participate in the study- Aged between 18 and 80 years of age- Clear optical media- Spherical equivalent +10D
DURATION	Single visit

REFERENCE DIAGRAM

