2. STUDY OBJECTIVES

- **Primary research objective** is to investigate the correlation and agreement between the intraocular pressure peaks detected during the water drinking test and the standard phasing test.

Secondary research objective is to correlate the IOPs obtained with both tests and prognostic outcome of the patients enrolled in the study to see whether these methods have predictive value for glaucoma progression. We will also measure autonomic nervous system activation (pupil size, heart rate and postural BP) during the test to investigate one possible mechanism behind it.

Lay summary

Raised intraocular pressure (IOP) is the main risk factor for the development and progression of glaucoma. The mDTC is a test that consists of four to five eye pressure measurements taken throughout office hours to check for rises in pressure that may be missed during their clinic appointment. To better try to assess the IOP peaks in a more time-efficient way, the water-drinking test has been developed. This involves the patient drinking a weight-adjusted volume of water within 5 minutes which has the effect of testing the ability to cope with increased demand for fluid to leave the eye. It is unclear as to the physiological mechanism by which this occurs. In this study we aim to compare the eye pressure measurements with both tests, and to see if either have any bearing on whether the patient's disease is getting worse. We also aim to show the changes in blood pressure and heart rate throughout the test.

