7. STATISTICS AND DATA ANALYSIS

7.1 Sample size

In this pilot study we aim to recruit a total of 40 glaucoma patients.

This is based on a power calculation of giving 80% power to detect a 2 mmHg difference in IOP peak (sd 2 mmHg) with $\alpha = 5\%$.

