7.4.3 Statistical analysis

No interim analyses will take place as part of this pilot study. Data will be acquired using integrated Heidelberg® software packaged with the Heidelberg® Spectralis OCT system. Data for this initial pilot study will be collected using Microsoft® Excel, and analysed using R and GraphPad prism to compare IOPs between the mDCT and WDT.

Specific analyses will include:

- Generation of baseline data including mean and standard deviation of baseline characteristics
- Bland-Altman agreement analysis of the primary outcome
- Correlation analysis between WDT and rate of progression.
- Analysis of change in OCT measurements
- Change over time analysis for secondary outcomes compared to baseline

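### Unit of analysis not stated: both eyes are assessed, and if they are analysed as independent rows the confidence intervals for the agreement results will be too narrow

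*Combined protocol and SAP*

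**What the plan says.** - Section 3.1.2 lists the baseline assessments, ending with IOP, and then says "All ophthalmic assessments will be done on both eyes"; the sentence ends by naming the Spectralis imaging system. A later sentence gives Goldmann applanation as the IOP method and does not say how many eyes are measured.
- The Aims row of the Study Summary words the comparison as one with the "modified diurnal tension curve in glaucomatous eyes".
- Section 2 makes it the primary objective to "investigate the correlation and agreement between the intraocular pressure peaks detected during the water drinking test and the standard phasing test".
- Section 7.1 counts people: "In this pilot study we aim to recruit a total of 40 glaucoma patients".
- Section 4.1 sets the glaucoma criterion for the patient, not for each eye.
- Section 7.4.3 lists "Bland-Altman agreement analysis of the primary outcome" and, as its only correlation, WDT against rate of progression.

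No section gives a study-eye rule, averaging of the two eyes, a patient-level term, or any other method for two eyes from one person.

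**The concern.** The two eyes of one patient share systemic physiology, the time of day, the same water load and the same observer. Their WDT-minus-mDTC differences are therefore likely to be positively correlated. A standard Bland-Altman or correlation routine treats each row as an independent subject. If every eye is entered as a row, n is taken as 80 when the independent units number 40.

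In an agreement study the main results are the bias, the limits of agreement and how precisely each is known, so overstated precision bears directly on the conclusion. Leaving the unit open also allows right eye, left eye, worse eye, mean or all eyes to be chosen after the results are seen. Finally, because eligibility is set per patient, a fellow eye without glaucoma could enter an analysis that is meant to describe glaucomatous eyes.

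**Working it through.** **The plan's own figure.** Section 7.1 gives 40 patients for 80% power, a 2 mmHg difference, SD 2 mmHg and alpha 5%. Two-sided t-test calculations need 10 patients if 2 mmHg is the SD of the paired difference, or 34 in total for two independent groups. Neither is 40, and the text does not say whether the SD is per eye or per patient. So the calculation does not reveal the intended unit, and the rest of the check does not depend on it.

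**Inputs**
- SD of the peak difference, from the limits of agreement cited in section 1.1.6 (-3.9 to 8.2 mmHg): (8.2 + 3.9)/(2 × 1.96) = 3.09 mmHg.
- Patients: 40 (section 7.1), hence up to 80 eyes.
- Between-eye ICC of the differences, ρ: not in the documents. Assumed, shown from 0.3 to 0.9.

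**Bias**
- Half-width with eyes taken as independent: 1.96 × 3.09/√80 = 0.68 mmHg.
- Correct half-width: the same figure × √(1 + ρ).
- Effective number of eyes: 80/(1 + ρ).

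**Each limit of agreement**
- Correct half-width: 1.96 × 3.09 × √[(1 + ρ)/80 + 1.96²(1 + ρ²)/(2 × 79)].
- With eyes taken as independent (ρ = 0 in the formula): 1.16 mmHg.

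Coverage of the nominal 95% intervals comes from 20,000 simulated studies of 40 patients with two eyes each.

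| ρ (assumed) | Effective eyes | Correct half-width, bias (naive 0.68) | Coverage of naive CI, bias | Correct half-width, limit (naive 1.16) | Coverage of naive CI, limit |
|---|---|---|---|---|---|
| 0.3 | 61.5 | 0.77 | 91% | 1.25 | 93% |
| 0.5 | 53.3 | 0.83 | 88% | 1.34 | 91% |
| 0.7 | 47.1 | 0.88 | 86% | 1.45 | 88% |
| 0.9 | 42.1 | 0.93 | 85% | 1.57 | 85% |

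With one value per patient (the mean of the two eyes), simulated coverage for the bias was about 95% throughout.

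**Point estimates.** With two eyes from every patient, the mean difference is unbiased whatever ρ is. The pooled variance has expectation SD² × (1 - ρ/79). At ρ = 0.9 that is a shortfall of 0.9/79 = 1.1%, so the limits themselves barely move. The fault is confined to the intervals around them.

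**Secondary correlation with progression.** Under no association, pooling eyes inflates the variance of the correlation coefficient by about 1 + ρ₁ρ₂, where ρ₁ and ρ₂ are the between-eye ICCs of WDT peak and progression rate. If both equal 0.3, 0.5, 0.7 or 0.9, the factors are 1.09, 1.25, 1.49 and 1.81. A nominal 5% test then has true size of about 6%, 8%, 11% and 15%, in agreement with simulation. With unequal ICCs the inflation is smaller: simulated size was 6.6% for 0.5 and 0.3, 7.5% for 0.7 and 0.3, and 8.2% for 0.9 and 0.3.

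**The case against.** The strongest reply is that the plan nowhere says that 80 eyes will be pooled. Sections 3 and 7.1 count patients, and one value per patient is consistent with that. On that reading there is no undercoverage. This stands: the defect is an unstated unit of analysis, and the narrowing is conditional on how the gap is filled. A reader might infer that the primary intervals are bound to be too narrow. The documents do not support that.

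Second, the both-eyes sentence names an imaging device, and tonometry is described separately. This stands in part. Two-eye IOP is an inference, though a natural one: IOP closes the list of assessments to which that sentence refers, and the Study Summary speaks of eyes. For OCT, one of the planned measures of progression, both eyes are explicit.

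Third, a reader might take the correlation figures as bearing on the primary result. Section 7.4.3 lists a correlation only for progression, which is secondary. Section 2 does include correlation of the two peaks in the primary objective. If that correlation is added, the same care is needed.

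Fourth, the effect is modest: about 0.1 to 0.25 mmHg on the half-width for the bias, against cited limits spanning 8.2 + 3.9 = 12.1 mmHg, in a self-described pilot. That is fair, and power is not at risk either, since even at ρ = 1 the effective sample is 40. But coverage of 85% to 91% under a 95% label is still wrong and easily avoided.

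**Conclusion.** The point holds as a conditional one. The plan has both eyes assessed and does not state the unit of analysis or how between-eye correlation is handled. If eyes are analysed as independent rows, the CI for the bias is too narrow by a factor of √1.3 = 1.14 to √1.9 = 1.38, and CIs for the limits of agreement are too narrow by a factor of 1.08 to 1.36. The secondary progression test is anti-conservative to the extent shown above.

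The direction holds for any positive between-eye correlation. The size rests on the assumed ICC range, on an SD taken from a cited study that reports by eye, and, for the correlation, on both variables sharing the same ICC. Neither a distorted bias estimate nor a loss of power follows from the pairing. The possible entry of fellow eyes without glaucoma is a gap in the definition of the analysis set, and the documents give no figure from which to size it.

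**What to change.** Add a paragraph to section 7.4.3 that:

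1. makes the patient the independent unit and states whether IOP is taken and analysed for both eyes;
2. includes only eyes that themselves meet the glaucoma definition;
3. models the difference as mean + patient random effect + eye residual, with limits of agreement = mean ± 1.96 × √(patient variance + eye variance) and CIs from a bootstrap that resamples patients;
4. applies the same patient-level clustering to the correlation and progression analyses.

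A pre-specified single study eye or the patient mean is an acceptable simpler alternative. Each has a price. A single eye gives a half-width for the bias of 1.96 × 3.09/√40 = 0.96 mmHg. Limits based on patient means describe an average of two eyes, and their SD is smaller by √((1 + ρ)/2), which is 0.87 at ρ = 0.5, so they should not be read as limits for one eye.

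The cost is one paragraph and a few lines in R, which the plan already names. No further data, visits or patients are needed. The downside is slightly wider intervals than naive pooling would report.

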1.1.2. IOP measurement methods

To provide more reliable data, twenty-four hour diurnal tension curves (DTC) can be measured. However, 24-hour IOP monitoring is unfeasible and time consuming in the majority of circumstances. The modified diurnal tension curve (mDTC) involving IOP measurements every 2 or 3 hours during office hours is therefore often used as a shorter alternative.

The water drinking test (WDT) is a tool that aims to indirectly evaluate the eye's aqueous humor outflow facility^{[8] [9]} by putting the drainage system under 'stress' in a test similar to that which may be used in cardiology or endocrinology. More recent research has suggested that water overload with the WDT may correlate well with the IOP peaks detected during a 24-hour intraocular pressure measure^[10].

It remains unclear as to the physiological mechanism behind this observed IOP rise. Several hypotheses exist including increases in outflow resistance^[11], episcleral venous pressure^[12], choroidal expansion^[13] and change in blood osmolality. However, it has been observed in one study that 20% of subjects developed change in IOP before change in osmolality could be detected.

Centrally mediated causes, possibly triggered by gastric expansion have been postulated with regards to activation of the autonomic nervous system^[14], but this has mainly been characterised in terms of cardiovascular physiology as oppose to intraocular pressure rise. Some evidence has been published to suggest the time course of the autonomic changes observed (rise in blood pressure, reduction in heart rate) are not consistent with reflex activity^[15], however in this study only 500mls of water was ingested over 3-4 minutes. This aspect of the test requires further characterisation in relation to the time profiles of the IOP rise.

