1.2 RATIONALE FOR CURRENT STUDY

The current method of using the mDTC is time consuming, labour intensive, and incomprehensive. Not only does the WDT have the potential to improve upon the time consuming and labour intensive nature of the test, but given the active element may improve diagnostic pickup and sensitivity for disease progression, given that the mDTC is only feasibly conducted during office hours.

Further work comparing the currently used mDTC and the WDT to assess IOP peak and fluctuation is necessary. The study mentioned above^[24] showed strong evidence of the clinical applicability of the WDT and its correlation with the mDTC. Furthermore, the IOP peak obtained by the WDT has been proved to be an independent risk factor for the development and progression of glaucoma^[5,8]. However, to date, there are no studies focusing on OCT data that will indicate progression of 'pre-perimetric' glaucoma, or any studies focusing on the most commonly referred group of patients referred for the test. This will aid us to discern the best way to assess IOP peaks and manage glaucoma treatment and progression.

Our hypotheses are:

- The peak IOP during the WDT correlates with mDCT
- Peak IOP during the WDT is associated with rate of glaucoma progression as measured with OCT
- Changes in autonomic variables associated with IOP rise are consistent with a autonomic reflex as the physiological mechanism behind the test.

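### The 15-minute autonomic schedule has no reading specified during drinking and no stated time for the first post-water reading, so it is too coarse to date autonomic onset relative to drinking; hypothesis 3 can be tested only for changes that persist to a scheduled reading.

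*Combined protocol and SAP*

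**What the plan says.** **The mechanism question.** Section 1.1.2 raises a centrally mediated cause, possibly set off by the stomach filling. It then cites some evidence that the timings seen after water "are not consistent with reflex activity", noting that the cited study gave only 500 mL over 3 to 4 minutes. It concludes: "This aspect of the test requires further characterisation in relation to the time profiles of the IOP rise". The third hypothesis in section 1.2 is: "Changes in autonomic variables associated with IOP rise are consistent with a autonomic reflex as the physiological mechanism behind the test". The secondary objective in section 2 is to measure autonomic activation while the test is under way.

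**The schedule.** Section 3.1.2 has the patient "drinking 800mL of water at room temperature, within a maximum of five minutes". For IOP, "For the WDT, the first IOP measure will correspond to the last mDTC measure", and then "three IOP measurements will be made after water intake with a 15-minute interval between each". For the autonomic variables, "At each 15 minute interval, postural blood pressure, heart rate, oxygen saturations and pupil diameter will be measured".

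**Baseline.** The same-day assessments in section 3.1.2 include "ophthalmic examination, postural blood pressure measurement, testing of visual acuity". Heart rate and pupil diameter are not in that list.

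**Elsewhere.** Section 4 says only that measurements follow the water drinking test. Appendix 1 lists the procedures without finer timing. Section 7.4.3 plans a change-over-time comparison with baseline for secondary outcomes and names no analysis of onset.

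**The concern.** The protocol treats timing as evidence on mechanism. A trigger tied to gastric filling predicts a change that begins while the patient drinks or very soon after. The schedule specifies no reading during the drink and leaves the first reading after it undefined.

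Two things are at stake. If no autonomic change is recorded, the reason could be that there was none or that a short response settled before the first reading. If a change is recorded, it cannot be dated closely enough to tie it to the drink rather than to a slower route acting some minutes later. In either case the study would have little to say on onset, which is the feature section 1.1.2 uses to judge a reflex.

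**Working it through.** The documents give no sample size, power or precision figure for hypothesis 3, so there is no stated figure to reproduce. The check is of what the schedule can resolve.

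**Inputs (section 3.1.2).** Drinking lasts up to 5 minutes. There are three post-water time points 15 minutes apart. The delay from the end of drinking to the first point is not stated.

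**1. Readings available early on, under both schedules that fit the text**

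| Period | 0/15/30 min | 15/30/45 min |
|---|---|---|
| During drinking | 0 | 0 |
| Up to 10 min after drinking ends | 1 | 0 |
| Up to 15 min after drinking ends | 2 | 1 |

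**2. Window in which onset can be placed.** Under 15/30/45, a change first seen at 15 minutes could have begun at any time since drinking started. The window is 15 minutes plus the drinking time: 15 + 0 = 15 to 15 + 5 = 20 minutes. The 15-minute step is 15/5 = 3 times the longest drinking period. Under 0/15/30, a change seen at the end of drinking is placed within the drink itself, at most 5 minutes, provided there is a pre-water value to compare it with. A later onset is placed only within a 15-minute step.

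**3. How much of a brief response would remain.** The documents give no duration for such a response. As an assumption, let it decay exponentially with constant τ, so that the share left after t minutes is exp(−t/τ).

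| τ (assumed) | t = 15 min | t = 20 min |
|---|---|---|
| 2 min | 0.06% | under 0.01% |
| 5 min | 5.0% | 1.8% |
| 10 min | 22% | 14% |
| 15 min | 37% | 26% |
| 30 min | 61% | 51% |

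Here t = 15 is a response that peaks as drinking ends, and t = 20 one that peaks at the start of a 5-minute drink, each first read 15 minutes after drinking ends. Short responses would be largely lost and long ones would be seen. Under 0/15/30, a response peaking as drinking ends is caught in full, because exp(0) = 1.

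**4. Order of autonomic change and IOP rise.** Take readings at 15/30/45 and a true lag of 10 minutes, with times counted from the end of drinking.
- Onsets at 2 and 12 minutes are both first seen at 15: recorded lag 15 − 15 = 0.
- Onsets at 10 and 20 minutes are first seen at 15 and 30: recorded lag 30 − 15 = 15.

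The same true lag is recorded as zero or as one full step, depending on whether a reading falls between the two onsets.

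**5. Effect of minute-by-minute pulse.** Over 5 minutes of drinking plus 15 minutes after it, this gives about 20 readings at 1-minute resolution, where the plan has one (15/30/45) or two (0/15/30). It dates pulse change relative to drinking. It does not date the IOP rise any better, because IOP stays on its 15-minute grid.

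**The case against.** The strongest reply is that the plan promises less than the concern assumes. The hypothesis speaks of consistency with a reflex, the objective of investigating one possible mechanism, and the lay summary in section 2 of showing blood pressure and heart rate changes over the test. None of these commits the study to measuring latency. It is a secondary aim in a 40-patient pilot. Autonomic readings share the IOP time points, so direction, size and association with IOP can be examined. The documents give neither the speed nor the duration of the reflex in question, so the amount missed cannot be known from them.

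Most of this stands, and it rules out several stronger conclusions that a reader might draw:

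- *That there is no reading when drinking ends.* The text fixes the spacing but not the first time, and 0/15/30 fits as well as 15/30/45.
- *That autonomic measurement occurs only after the water.* Postural BP is listed at the baseline assessment.
- *That hypothesis 3 cannot be tested at all.* It can, for changes still present at a reading.
- *That every lag under 15 minutes is recorded as zero, or that late and early responses always look alike.* This is true only when both onsets fall within the same step.

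The reply does not remove the core of the point. Section 1.1.2 itself reasons from time course and says the time profile needs characterising, and no section of the plan specifies a reading during the drink.

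**Conclusion.** The point holds in a limited form. The schedule is too coarse to date the onset of autonomic change relative to drinking. No reading is specified during the drink under any interpretation, and the window for onset is 15 to 20 minutes if the first reading comes 15 minutes after drinking ends. Hypothesis 3 can therefore be tested only for changes that persist to a scheduled reading.

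The resolution result follows from the schedule alone. The loss of a brief response (0.06% to 61% remaining at 15 minutes) rests on the assumed 15/30/45 timing and an assumed τ of 2 to 30 minutes, and should be read as a range of possibilities rather than an estimate. The primary comparison of IOP peaks is unaffected. This is a low-cost improvement to a secondary objective, worth making because it changes what the study can say about mechanism.

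**What to change.** In section 3.1.2:

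1. State when the first post-water reading falls, counted from the end of drinking.
2. Keep the pulse oximeter, already used for saturations, on from just before drinking. Record pulse and saturation each minute during drinking and for the first 15 minutes after it.
3. If practicable, add one BP and pupil reading at the end of drinking, with BP taken in the same posture as a baseline reading so that the two are comparable.
4. Leave the IOP schedule unchanged, and say that conclusions will concern autonomic onset relative to drinking. The order of autonomic change and IOP rise stays limited to the 15-minute IOP grid.

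If this is not done, reword hypothesis 3 (section 1.2) and the secondary objective (section 2) as a description of sustained autonomic changes and their association with IOP, with no claim for or against a reflex based on onset.

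The cost is a wording change and a few more rows on the data collection form, using equipment already in the plan. The downside is slightly more recording in the first 15 minutes. The rewording alternative adds no measurements.
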